Without question, statin therapy is extremely effective at lowering LDL-C and risk for CVD in high risk populations, and, in general, statins are well-tolerated (18). Muscle fatigue, pain and weakness are idiopathic but well known potential side effects. Less appreciated is the fact that statins also increase the risk of developing insulin resistance/type 2 diabetes (6-9, 19-21) and attenuate the beneficial effects of exercise on cardiovascular adaptations and fitness (13). In fact, statins when combined with exercise increase the risk and severity of adverse muscle reactions (22-24). This interaction effect is of obvious concern given the importance of physical activity in the clinical treatment of patients with type 2 diabetes and/or CVD. Although the mechanism(s) underlying the side effects of statins is unknown, there is evidence that the impact of statins on skeletal muscle may be progressive. In the only direct comparative cohort study between patients on statins and matched controls, duration of statin therapy (< 10 vs. \geq 10 months) was found to increase the risk of developing muscle-related side effects (5), which is consistent with clinical reports of some patients experiencing symptoms only after years of

statin therapy (25). Perhaps most alarming, mounting evidence, including preliminary data in this application, indicates that statins directly compromise mitochondrial respiratory function, providing a potential unifying mechanism for the dose- and duration-dependent complications associated with statin use. Clinically, because the loss of aerobic capacity with age (Fig. 1)(1) is an independent risk factor for morbidity and mortality (26,27) a direct inhibition of respiratory function induced by statin therapy would be expected to shift this relationship (see redline) and hasten the decline in aerobic capacity needed to support daily living (Fig. 1). This is especially alarming given that the greatest increase in statin prescription is predicted to occur in adults >60 years of age who already have low aerobic capacity(3) and that statin therapy is being widely advocated for younger individuals, meaning that lifetime statin use may potentiate aging induced loss of aerobic capacity (28). Thus, while the risk for CVD undoubtedly favors statin

[figure not shown]

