- iv. Fasting Blood Draw: Glucose, insulin, total cholesterol, HDL-C, LDL-C, triglycerides, creatinine, CK, and ALT will be measured in fasting blood samples.
- v. Insulin Sensitivity: Glucose and insulin, and insulin sensitivity will be calculated using a minimal model program following the IVGTT.
- vi. Cardiovascular Function: Heart rate and stroke volume (and finometer) will be measured under resting conditions.
- **B. Study Type and Design:** This study is a longitudinal, repeated measures, double-blinded design with participants randomly assigned to placebo, low (20 mg/d) or high (80 mg/d) atorvastatin therapy for a one year dose-response study. We expect to screen approximately of 500 participants to enroll (randomize) a maximum of 60 participants. The goal is to have 45 participants complete all study procedures (15 in each group). Repeated measures design allows each subject to serve as their own control. Placebo groups are included to account for potential changes in muscle mitochondrial function independent of statin therapy over the 1 year dose-response.

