for 10% dropouts. The subject enrollment will be split equally between the two sites (15 participants/group per site). For this study, our primary analysis is to use mixed model to test the interaction between group and time, which is expected to be more powerful than the two-sample t-test because all repeated measurements will be considered in modeling, baseline patient characteristics can be controlled statistically, and participants with missing data can be included for analysis.

D. Subject Criteria

a. Inclusion criteria/Exclusion criteria:

- i. Inclusion Criteria
 - Ages 35–65 years
 - BMI between 25-43 kg•m²
 - >5% risk for a cardiovascular event in the next 10 years according to the 2013 American College of Cardiology/American Heart Association risk calculator and/or 2 out of 5 metabolic syndrome risk factors (Triglycerides ≥ 150 mg/dL; HDL ≤ 40 mg/dL; Glucose ≥ 100mg/dL; Waist Circumference ≥ 102cm for males, 88cm for females; Blood pressure: ≥ 130mmHg systolic and/or 85mmHg diastolic or being treated for hypertension) and/or LDL-Cholesterol >120 mg/dl.
 - Stable doses of medications for 90 days
 - Willing to stop all NSAIDs and aspirin for 7 days prior to muscle biopsy

[figure not shown]
ii. Exclusion Criteria

- Smoking
- Previous use of statins
- Use of other medications or supplements that affect lipid profiles or body weight in the last 6 months
 - o e.g., fibric acids, bile acid sequestrants, nicotinic acids, fish oil
- Diagnosis of chronic diseases including CVD, other metabolic diseases (e.g., thyroid), current diagnosis and active treatment of cancer, HIV, or acquired immunodeficiency syndrome.
- Diagnosis of type 1 or type 2 diabetes at the time of screening (fasting blood glucose >126mg/dL). If evidence of type 2 diabetes outcome measures is detected during the course of the study (fasting glucose > 126 mg/dl or HbA1c > 6.5%) we will notify the participant to contact their physician.
- History of abnormal bleeding problems
- Currently taking (within the last 10 days) anti-platelet medication (Plavix), Warfarin, and other anti-coagulants (eliquis, pradaxa, and xarelto) medications.
- >2 fold upper normal limit (UNL) for ALT or creatinine
- Women who are pregnant or breastfeeding
- Individuals with polymorphism (SLCO1B1) known to be associated with susceptibility for statin induced myopathies (tested at screening)
- Currently enrolled in another research study

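### The on-study diabetes notification rule names HbA1c >6.5%, but no written test list includes HbA1c; add it to the month 6 and 12 fasting draws

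*Combined protocol and SAP*

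**What the plan says.** The diabetes bullet in II.D.a.ii (Exclusion Criteria) holds two rules. The entry rule is "Diagnosis of type 1 or type 2 diabetes at the time of screening (fasting blood glucose >126mg/dL". The on-study rule applies if evidence of type 2 diabetes is detected during the trial: "fasting glucose > 126 mg/dl or HbA1c > 6.5%) we will notify the participant to contact their physician". Its two criteria are joined by "or" in the plain sense: either is enough, and the action is advice to see a physician, not withdrawal or a dose change.

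The objectives (II.A.b.iv) list the fasting tests: "Glucose, insulin, total cholesterol, HDL-C, LDL-C, triglycerides, creatinine, CK, and ALT will be measured in fasting blood samples". The IVGTT section (II.E.a.iv) repeats the fasting draw at months 1, 6 and 12. The blood-draw section (II.E.a.ii) lets the study physician request further laboratory tests for safety, with an additional visit if needed, but names no analyte, trigger or time.

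On diabetes risk, the background (I.B) says: "Less appreciated is the fact that statins also increase the risk of developing insulin resistance/type 2 diabetes". II.F.b presents help with later decisions about diabetes risk as a benefit of taking part.

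**The concern.** A threshold in a safety rule is useful only if the quantity is measured. Here one of two thresholds has no planned measurement. The HbA1c criterion adds something only for a person whose fasting glucose does not cross its own limit, and nothing written would prompt an HbA1c test in that person.

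At stake is a notification: such a participant could complete a year of study treatment without being told to see a physician. The matter is relevant because the protocol itself says statins raise the risk of type 2 diabetes.

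**Working it through.** The plan gives no figure to reproduce. The check is a comparison of the rule with every written list of blood tests, followed by counts.

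**Step 1: where each quantity appears.** HbA1c occurs once in the document, in the II.D.a.ii rule.

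| Section | Tests listed | Glucose | HbA1c |
|---|---|---|---|
| II.A.b.iv, fasting blood (objectives) | glucose, insulin, lipids, creatinine, CK, ALT | yes | no |
| II.E.a.ii, screening draw | genetic markers, CK, GFR, ALT | no | no |
| II.E.a.ii, month 1 safety draw | myopathy, liver and kidney function | no | no |
| II.E.a.iv, fasting draw (repeated at months 1, 6, 12) | glucose, insulin, lipids | yes | no |
| II.E.a.iv, safety tests at months 6 and 12 | CK, ALT | no | no |
| II.F.a.ii, safety tests under statin risks | CK, ALT | no | no |
| V.C, results shared with participants | includes IVGTT glucose and insulin | yes | no |

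**Step 2: scheduled checks after randomisation.** II.B sets the size: "We expect to screen approximately of 500 participants to enroll (randomize) a maximum of 60 participants".

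- Fasting glucose: 3 per participant (months 1, 6, 12); 60 × 3 = 180 at most.
- HbA1c: 0 per participant; 60 × 0 = 0.

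These count written, scheduled tests. They do not count people missed.

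**Step 3: who falls in the gap.**

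- Fasting glucose above 126 mg/dL at screening: excluded at entry.
- Fasting glucose above 126 mg/dL on study: notified through the glucose criterion.
- HbA1c at or below 6.5% and glucose at or below 126 mg/dL: neither criterion is met.
- HbA1c above 6.5% and glucose at or below 126 mg/dL at every scheduled draw: meets the rule as written, but no scheduled test would show it.

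Only the last group is affected. Its size would need the joint distribution of HbA1c and fasting glucose in this population, which the documents do not give.

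**Step 4: number of assays if HbA1c is added.** On completion, II.B says: "The goal is to have 45 participants complete all study procedures (15 in each group".

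- Months 6 and 12: 60 × 2 = 120 at most; 45 × 2 = 90 if only the target completers reach both visits.
- One baseline test: 60 × 1 = 60. Total 120 + 60 = 180.
- II.C instead plans 30 per group, 30 × 3 = 90 participants. On that basis: 90 × 2 = 180 on study, and 90 × 3 = 270 with baseline.

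**Step 5: blood volume.** Assume an extra tube of 2-4 mL per test; the documents give no tube size. II.E.a.iv puts the total at about 622 mL.

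- Two tests: 4-8 mL; 4/622 = 0.6%, 8/622 = 1.3%.
- Three tests: 6-12 mL; 6/622 = 1.0%, 12/622 = 1.9%.

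**The case against.** The strongest reply is that no promise is broken. The rule is conditional: it says what to do with a result and does not commit to obtaining one. It already operates through fasting glucose. The physician's option to add tests means an HbA1c value could arise, and adverse-event enquiries at testing visits and by telephone (II.K.c) could bring in a value from ordinary care. Having a threshold ready for such a value is coherent drafting. All of this stands, and it rules out the inference that the rule as a whole does not work or that HbA1c can never trigger it. What remains is that neither route is planned for this purpose, and neither is prompted when glucose is unremarkable.

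A second reply is that absence from a list is weak evidence. The written lists do not fully agree: the screening draw in II.E.a.ii omits the glucose and lipids that eligibility needs, and the fasting draw in II.E.a.iv omits the creatinine listed in II.A.b.iv. A figure is also missing from the extracted text of II.D.a. This stands too, and limits the claim to what is written. The lists do agree in leaving HbA1c out. If an operational schedule already includes it, one added line settles the matter.

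A third reply is that participants receive their IVGTT glucose and insulin results. They do, so they are not left without glycaemic information. But V.C places this at the end of participation, so it does not replace notification during the study.

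**Conclusion.** The point holds in a narrow form. One of the two criteria in the notification rule has no scheduled measurement: three fasting glucose checks per participant after randomisation against no HbA1c check. It is a minor participant-safety gap, confined to people with HbA1c above 6.5% and fasting glucose at or below 126 mg/dL, in unknown number. It rests on the written lists being the actual test plan.

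Two stronger readings are tempting, and the documents support neither.

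- A reader might infer that the entry criterion is defective because it uses fasting glucose alone. The entry and on-study rules serve different purposes, and a difference between them is not an error. The other laboratory exclusions (">2 fold upper normal limit (UNL) for ALT or creatinine" and "Individuals with polymorphism (SLCO1B1) known to be associated with susceptibility for statin induced myopathies (tested at screening") are separate bullets that do not bear on diabetes.
- A reader might infer that undetected diabetes would distort the insulin-sensitivity comparison. Notification is not an endpoint and does not remove anyone from the study. No effect follows for the primary outcome or for any analysis.

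**What to change.** Add HbA1c to the fasting draws at months 6 and 12 in II.A.b.iv and II.E.a.iv. Preferably test once at baseline as well, so that a later value can be interpreted. Apply the existing 6.5% notification limit and add the value to the shared results in V.C. Baseline testing already precedes randomisation (II.E.a.xiv), so no extra visit is needed.

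For 60 randomised the cost is at most 120 on-study assays, or about 180 with baseline. Under the assumed tube size it is 4-12 mL more blood per participant.

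Deleting the HbA1c criterion would cost nothing and would align the wording with the tests, but it would not address the safety point. If the physician did obtain a value above 6.5% with unremarkable glucose, no written rule would then call for notification. An HbA1c entry exclusion is not recommended: the point does not need it, and running it on the screening sample could mean up to about 500 assays, the number expected to be screened.

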- v. Muscle biopsy: After an overnight fast, the participant will complete a survey to confirm the absence of bleeding disorders, and avoidance of NSAIDs and aspirins for 7 days prior to biopsy. Participants will then lie on a table in a supine position. A location on the mid-thigh will be identified. The area will be properly shaved and then thoroughly cleaned using sterile techniques (alcohol and iodine). A sterile drape is then placed over the leg with the biopsy site showing through a fenestration in the center of the drape. A numbing agent will be lightly sprayed onto the biopsy location (ethyl chloride) immediately before the skin, adipose, and muscle fascia is anesthetized with lidocaine (1-2% HCL) or diphenhydramine 1% injectable solution for those with 'caine' allergies. After allowing 1-2 minutes for the site to become numb the skin and fascia is incised with a sterile scalpel (#11). The Bergstrom needle (5mm) is then placed through the incision into the vastus lateralis muscle. Suction is applied to the proximal port of the needle, and the tissue is cut rapidly with the internal portion of the needle, and the entire needle

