is removed from the incision. Sterile gauze is placed on the incision site and pressure is applied with an ice pack for ~5 minutes. The site is then closed with a steri-strip and band-aid. Sterile gauze is then applied on top of the band-aid and pressure is applied by wrapping coban around the thigh. Approximately 100-200 mg of skeletal muscle will be collected during each biopsy in one pass. In the case where less muscle is harvested per pass, one more additional pass will be taken with the participants consent. The tissue collected is dissected free of connective tissue and separated for mitochondrial function studies or frozen in liquid nitrogen for subsequent biochemical analyses as done previously (13, 61). [name] and his team have performed over 300 skeletal muscle biopsies without incidence since starting his independent lab in 2005. Additionally, Neurologists who study various muscle diseases regularly perform the technique at KUMC. After analysis for current project is complete any remaining muscle samples will be stored indefinitely for future research. Muscle biopsies will be repeated at 1, 6, and 12 months. See appendix for letter from IRB Director ([name]) at [name] previous institution (MU) stating his record for conducting muscle biopsies and a letter of support for the procedure from [name], the Director of the CTSU. Biopsies will be taken by [name] or by [name] who has been trained during his PhD work at Oregon State and by [name] here at KUMC

- vi. Near Infrared Spectroscopy (NIRS): Muscle mitochondrial functional capacity will be measured non-invasively using a NIRS technique developed by [name], a member of the research team at ECU (46). Participants will perform submaximal knee extension exercise to increase muscle oxygen consumption (mVO₂) and the recovery kinetics is determined during a series of repeated arterial occlusions. The mVO₂ data are fit to a mono-exponential function to calculate the rate constant, which is directly related to the mitochondrial respiratory capacity. NIRS will be repeated at 1, 6 and 12 months.

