- ii. Statins: Statin therapy is associated with muscle issues that range from more minor issues of muscle pain, cramping and fatigue, to myopathies, to the very severe issues of rhabdomyalgia, although this is rare. Statins are the most prescribed drug in the world. Statins are also associated with headaches, nausea, and constipation. Statins are also not well tolerated by athletes suggesting that exercise may worsen the effects of statins on skeletal muscle. Thus, there is the potential that participants in our study may have adverse effects while taking statins. A recent trial conducted by our consultant, [name], utilized 80 mg/day of atorvastatin and found that ~15% of participants experienced pain and weakness (2). atorvastatin 80 mg is an increasingly common dose because three large clinical trials, REVERSAL (atorva 80 v. prava 40, n=502) (3), PROVE IT (atorva 80 v. prava 40, n=4,162) (4), and TNT (atorva 80 v. prava 10, n=10,001) (5) demonstrated reduced atherosclerosis and cardiac events with atorvastatin 80 mg. These studies were done in CAD patients, a group on multiple other medications and likely to be at higher risk for side effects than our healthy participants. Nevertheless, side effects were rare. Liver function test (>3 times upper normal limits [UNL]) and creatinine kinase (CK) elevations (> 10 UNL) occurred in only 1-3.3% of patients treated with atorvastatin 80 mg for up to 24 months, respectively. These side effects should be even more rare given that we will pre-screen and exclude individuals with polymorphisms (GATM and SLC01B1) that increase risk for myopathy. We will test both muscle enzymes (creatine kinase) and liver enzymes (ALT) to determine if statins are causing either muscle myopathies or liver injury. This testing will occur at baseline and at 1 month into taking statins. If enzymes are elevated, the subject will be taken out of the study for their own health. Finally, study physicians at both KUMC who commonly prescribe statins and deal with patients who experience statin induced problems will provide medical coverage for our studies. Participants are free to abstain from taking their statins and leave the study at any time. Importantly, most individuals report that statin induced complications go away very quickly after stopping the therapy. Participants who are discontinued from the study for a medical reason judged to be appropriate by the study doctors will receive the same reimbursement as if they completed the study to avoid the possibility that a subject would "soldier on" simply for the reimbursement.

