- iii. Muscle Biopsies: Acute issues of muscle tightness, soreness, and bruising can be associated with muscle biopsies. More severe problems include the risk of infection. To avoid these issues the biopsy procedures will be conducted with sterile techniques with medical supervision. Moreover, the participants are given detailed instructions including how to take care of the incision site and who to contact should anything seem abnormal.
- iv. IVGTT Catheter Placement and Venipuncture: Their risk is very minimal. However, certain risks including discomfort, blood clot, minor bleeding, bruising, infection,

and redness can occur. Aseptic techniques will be used to minimize such risks. Risks of bruising and minor pain can occur with venous phlebotomy. Venous catheter placements can rarely cause bleeding, bruising, soreness, and infection. Risk of bleeding after removal of the line also is possible. Infusion of glucose or insulin may cause the subject to feel nauseous or flushed. Drinks and snacks will be available for the participants at the completion of the IVGTT should they have low blood sugar or feel nauseous.

- v. DEXA: The DEXA scan may make participants slightly uncomfortable because you have to hold very still. This research study involves exposure to radiation equal to the radiation that most Americans receive in about 2 days from background radiation, such as naturally occurring radioactivity in the soil and air. The risk from radiation exposures of this magnitude is too small to be measured directly and is considered to be very low when compared with other everyday risks.
- b. Potential Benefits: All participants will gain health information about themselves. At the end of the study, results collected will be shared with the subject in face-to-face meetings. Moreover, although we are studying the impact of statins on muscle health, statins overall do have a strong track record of lowering blood lipids and in most trials lowering cardiovascular risk. Moreover, the health information gained throughout the study will aid the participants in making future medical decisions with their physicians in relation to cardiovascular and diabetes risk.

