 - c. Providing on-going information to the study sponsor and the IRB: PI, Study Coordinator
 - d. Maintaining participant's research records: PI, Study Coordinator
 - e. Completing physical examination: PI, CTSU Nurse
 - f. Taking vital signs, height, weight: CTSU Nurses
 - g. Drawing / collecting laboratory specimens: CTSU Nurses
 - Performing / conducting tests, procedures, interventions, questionnaires: PI,
 Study Coordinator
 - i. Completing study data forms: Study Coordinator
 - j. Managing study database: PI

K. Assessment of Subject Safety and Development of a Data and Safety Monitoring Plan

- **a. Key personnel:** [name], [name], [name], [name], study physician at KUMC and [name], study physician at ECU.
- b. Plan for safety monitoring and review: [name] will serve as the Chair of the Data Safety Monitoring Board and will convene every 6 months with the other members, Drs. [name] and [name] to make decisions on safety of the participants. Enrollment data will also be reviewed twice a year by the DSMB. In addition, data will be reviewed on a yearly basis with the biostatistician, [name] to determine if the studies should be shortened do to either no measured effect or due to effects that are greater than what power calculations indicated. If problems occur with participants, blinded study staff will alert [name]. [name] will have access to dose and type of statin and will consult the study physicians/cardiologist to make a decision on whether the subject should be removed from the study for safety concerns. The PI and other key personnel will be examining research data on a subject to subject basis to ensure it is accurate and to address any potential problems that may arise with the protocols. In addition, Drs. [name] and [name] will discuss data at least once per month through in person meetings or by phone to ensure that data collection is occurring in a consistent manner at both locations.
- **c. Plan for adverse event reporting:** Adverse events will be defined as any untoward medical occurrence in study participants or others immediately involved in the

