performance of the protocol, which does not necessarily have a causal relationship with the study treatment, but results in a change in intervention, daily function, hospitalization or rated category 3 or above using the National Cancer Institute Common Terminology Criteria for Adverse Events (CTCAE) v3.0. Expected events such as slight muscle soreness consistent with statin therapy, or those consistent with a participant's prior medical history not sufficient to alter the intervention will not be considered an AE. Staff involved in performance of the protocol (e.g. coordinators) will continually monitor participants for adverse events throughout the intervention, and study staff will assess adverse events at every testing visit as well as during regularly scheduled telephone assessments with all randomized participants.

If study staff, tester, or participant reports adverse events or complaints, relevant information will be collected and documented. The participant will be evaluated by the unblinded investigator identified in the protocol. The investigator will determine the severity (according to the CTCAE) and relatedness of the AE to the intervention. The investigator will identify adverse events of clinical concern, those that may require further workup, or suggest that additional participation in the intervention might be a safety risk. These AEs will first be discussed with the participant and then communicated to the study staff or providers with participant's consent and as appropriate. Serious adverse events directly related to the intervention will be reported immediately to the IRB. Any adverse event rate over 30% in 12 months will be reported to the NIH.

III. Subject Participation

A. Recruitment:

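### The pre-biopsy survey, as described, does not ask about the antiplatelet and anticoagulant drugs that bar entry, and no written step asks about them before the month 1, 6 and 12 biopsies

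*Combined protocol and SAP*

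**What the plan says.** Among the exclusion criteria (II.D.a.ii) is "Currently taking (within the last 10 days) anti-platelet medication (Plavix), Warfarin, and other anti-coagulants"; the list goes on to name Xarelto, Eliquis and Pradaxa. A history of abnormal bleeding is a separate criterion in the same list. The inclusion criteria add a willingness to stop NSAIDs and aspirin for 7 days before a biopsy.

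Concurrent medications are collected in the telephone screen, ahead of in-person screening (II.E.a.i).

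For the biopsy itself, II.E.a.v says that "the participant will complete a survey to confirm the absence of bleeding disorders, and avoidance of NSAIDs and aspirins for 7 days prior to biopsy". The same section says "Muscle biopsies will be repeated at 1, 6, and 12 months", in addition to the baseline biopsy.

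Other sections offer indirect protection:

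- II.F.a.iii says "the biopsy procedures will be conducted with sterile techniques with medical supervision".
- II.K.c says "study staff will assess adverse events at every testing visit as well as during regularly scheduled telephone assessments with all randomized participants".
- II.K.b has blinded staff report problems to a designated person with access to the allocation, who consults the study physicians to "make a decision on whether the subject should be removed from the study for safety concerns".
- II.F.a.ii refers to "Participants who are discontinued from the study for a medical reason judged to be appropriate by the study doctors", in the context of their payment.

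**The concern.** The protocol treats recent use of these drugs as a reason to keep a person out of a study built around repeated muscle biopsies. That check is tied to entry, whereas most of the biopsies come later. The check placed next to the procedure covers bleeding disorders, NSAIDs and aspirin, but none of the drugs on the exclusion list.

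A participant prescribed clopidogrel or an anticoagulant at, say, month 4 has no bleeding disorder to report and may have taken no NSAID or aspirin. That person passes the survey as described and proceeds to a scalpel incision and a 5 mm needle with suction, possibly with a second pass. The population is aged 35 to 65 and can qualify through cardiovascular risk, metabolic risk factors or raised LDL cholesterol, so a new prescription within a year is plausible. What is at stake is an avoidable bleeding risk for a few people. The statistical conclusions are not in question.

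**Working it through.** **Text check.** The plan states no figure on this point, so the main check is to compare what each section requires.

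| Step | When | Asks about the listed antiplatelet and anticoagulant drugs? |
|---|---|---|
| Exclusion criterion (II.D.a.ii) | Entry | Yes, 10-day window |
| Telephone screen (II.E.a.i) | Before in-person screening | Concurrent medications in general |
| Pre-biopsy survey (II.E.a.v) | Biopsy | Not named; bleeding disorders, NSAIDs and aspirin only |
| Withdrawal criteria (II.D.b) | Follow-up | No; participant choice and raised CK or ALT |
| Medical supervision (II.F.a.iii) | Biopsy | No drug question specified |
| Adverse event review (II.K.c) | Testing visits and calls | No medication review mentioned |
| Removal for safety (II.K.b) | When a problem is reported | No; acts after the event |

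The bleeding-disorder item cannot stand in for the drug list, because the exclusion criteria treat bleeding history and these drugs as two separate entries. Adverse event review does not close the gap either. Under II.K.c an adverse event is an untoward medical occurrence that "results in a change in intervention, daily function, hospitalization or rated category 3 or above" on the CTCAE scale. A new prescription alone does not meet that definition, although the illness behind it might.

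**Illustrative size.** The inputs are biopsies at months 1, 6 and 12 (II.E.a.v), and a maximum of 60 randomised with a goal of 45 completers (II.B). The documents give no rate of new prescriptions, so 2% to 5% over 12 months is an assumption. Start times are taken as uniform, and every starter is assumed to stay on the drug and in the study.

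Biopsies still to come, by start time:

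- start in months 0 to 1: 3 remain
- start in months 1 to 6: 2 remain
- start in months 6 to 12: 1 remains

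Average per starter = (1 × 3 + 5 × 2 + 6 × 1) / 12 = 19/12 = 1.58.

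| Base | Follow-up biopsies | Starters at 2% | Biopsies on drug at 2% | Starters at 5% | Biopsies on drug at 5% |
|---|---|---|---|---|---|
| 60 randomised | 60 × 3 = 180 | 1.2 | 1.2 × 19/12 = 1.9 | 3 | 3 × 19/12 = 4.75 |
| 45 completers | 45 × 3 = 135 | 0.9 | 0.9 × 19/12 = 1.43 | 2.25 | 2.25 × 19/12 = 3.56 |

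As a share of follow-up biopsies: 1.9/180 = 1.06% and 4.75/180 = 2.64%. At a lower rate of 0.5%, 60 × 0.005 × 19/12 = 0.475, or about half a biopsy in the whole trial.

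**The case against.** The strongest reply is that the protocol sentence summarises a form that is not in the documents. A survey meant to screen for bleeding risk may well list these drugs. That possibility stands. If the form does ask, the sponsor only has to bring the protocol sentence into line with it.

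A second reply is that people with diagnosed cardiovascular disease are excluded, so a new anticoagulant would usually follow a new medical event. Such an event could come up in the adverse event review and reach the study physicians. This is a fair point and lowers the likely number exposed. It still leaves detection to an indirect route, with no requirement to ask before the needle goes in.

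Third, II.E.a.v describes local pressure, an ice pack and a compression wrap, and cites a record of more than 300 biopsies without incident; II.F.a.iii adds aftercare instructions. These measures bear on the consequences of a bleed but do not detect a drug. The record does not say whether any of those people were taking one.

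Finally, the 2% to 5% rate has no source in the documents, and the counts assume full persistence and no detection. Both points are correct. The counts are upper figures for whatever rate is chosen, and they give no estimate of harm. The omission itself does not depend on the rate.

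**Conclusion.** The concern holds. The plan sets out a specific pre-biopsy check which, followed as written, would clear a participant who has newly started a drug that bars entry. No other written step requires the question before the three follow-up biopsies. This is an omission covering drugs started after entry; it is not a contradiction between sections.

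The expected exposure is small: about 2 to 5 of up to 180 follow-up biopsies under the assumed rate, and fewer if the indirect safeguards work. Two limits remain. The survey form cannot be seen, and its use before each repeat biopsy is inferred from its place in the biopsy procedure. Sample size, type I error and the analysis model are unaffected. The change is worth making because it concerns participant safety and costs very little.

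**What to change.** Add the antiplatelet and anticoagulant list from II.D.a.ii, with its 10-day window, to the survey, and state in II.E.a.v that the survey is completed before every biopsy: baseline and months 1, 6 and 12. Refer any positive answer to the study physician before the procedure; the decision to proceed, delay or omit stays with that physician. If the biopsy is not done, record the reason and keep that visit's other measures, such as NIRS.

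The cost is one or two lines on an existing form and one protocol sentence. The downside is an occasional delayed or missed biopsy, and with it that visit's primary outcome; the mixed model in V.A does not require complete data.
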